# 9.2.2.4 Length of hospital stay (days)

Length of hospital stays will be considered as continuous outcome and summarized descriptively.

The median length of hospital stay will be compared between the treatment groups using a non-parametric method or a rank-ANCOVA analysis i.e., an ANCOVA analysis on rank-transformed data. For this analysis, the censoring rule in Section 8.6.4 will be used.

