#### 4. SAMPLE SIZE DETERMINATION AND RATIONALE

This is a randomized study with two treatment groups. The subjects will be randomized to the treatment groups (leronlimab or placebo) in a 2:1 ratio.

A total of three hundred ninety (390) subjects will be randomized in a 2:1 ratio to leronlimab or placebo groups with the goal of having 369 subjects (246 subjects in the leronlimab and 123 in the placebo group) complete the study.

The sample size is obtained based on the assumption that there will be a clinically meaningful difference in the rate of Day 28 mortality (i.e., 15% which is 45% Day 28 mortality rate for the placebo group versus 30% Day 28 mortality rate in the leronlimab group). This sample size is based on using a 2-sided Z-test with 80% power and an overall significance level of 0.05. The expected

dropout rate is 5%. To accommodate subject attritions due to the potential discontinuations, it is recommended randomizing an estimated 390 subjects (260 in the leronlimab group and 130 placebo group). Sample size is estimated using PASS sample size software, tests for two proportions.

A single arm, non-randomized, open-label phase is added to the protocol after completion of enrollment in the Randomized Phase of the study in order to provide access to leronlimab for the eligible patients. Approximately, 100 subjects are expected to be enrolled in the non-randomized phase. Enrollment will remain open until the decision is made by Sponsor and/or FDA to close the recruitment. No statistical power calculation is used for the sample size calculation for the non-randomized portion of the trial.

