## 8.4 Multiple Comparisons and Type I Error Rate Multiplicity adjustments

For the primary endpoint only one hypothesis will be tested, the final p-value will be adjusted as specified in Section 5.7 to protect the trial wise Type I error due to the interim analysis.

For the secondary endpoints, the hierarchical test procedure, with fixed sequence approach will be used to protect the trial-wise error rate. Please see Section 9.2.2 for the order of the secondary endpoints.

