#### 8.7.4 Censoring rule for subjects with outcome of Death

For analyses of length of stay (i.e., ICU or hospitalization) or duration of mechanical ventilation all deaths within 42 days will be considered censored at Day 42. Conceptually, a death corresponds to an infinite length of stay or MV support but censoring at any time greater than or equal to Day 42 gives the same answer as censoring at Day 42; both correspond to giving deaths the worst rank.

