# 9.2 Analysis of Efficacy Data

The primary analysis will be conducted on the mITT population. The PP population will be used as a supportive analysis if there is at least 5% difference between the numbers of subjects in the two populations. All statistical tests for efficacy will be two-sided tests, with  $\alpha$ =0.05

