#### 11. VERSION HISTORY

Changes incorporated into Version 2.0 of this document.

Editorial changes were made per Version 5.0 of the protocol.

Changes incorporated into Version 3.0 of this document.

Safety assessment at an interim per the LOA dated 06 Jul 2020.

Changes incorporated into Version 4.0 of this document.

- Efficacy Interim Analysis to be conducted after 50% (~195 subjects) have been randomized and completed 4 weeks of randomized treatment instead of 2 weeks of treatment per the request from the DSMC, since the primary endpoint is Mortality at Day 28.
- Descriptive summary of key outcome indicators such as, change in clinical status based on a 7 point ordinal scale, and total duration of hospitalization, ICU, and mechanical ventilation use added as part of the interim report to be shared with the DSMC.

Changes incorporated into Version 5.0 of this document.

- A single arm, non-randomized, open-label phase added to the protocol after completion of enrollment in the Randomized Phase of the study. Up to 100 subjects will be enrolled in the non-randomized phase.
- Proportion of patients achieving a category of 6 or higher at Days 14 and 28 (on a 7 point ordinal scale) was added to Secondary Endpoint
- Length of hospital stay (days) was moved from Exploratory Endpoint to Secondary Endpoint
- Change from baseline in Sequential Organ Failure Assessment (SOFA) score at Day 14 was moved from Secondary Endpoint to Exploratory Endpoint
- All- cause mortality at Day 42 was added to Exploratory Endpoint
- Section 9.4 Analysis of Safety Data was added

Changes incorporated into Version 5.0 Amendment of this document (Version 6.0).

- ITT population is updated to mITT population in Section 8.6 and 9.2

- Section 7.3 PP Population more clarification added to the description of the major protocol violations.
- Section 8.5 Subgroups were updated to be in line with what is stated in the protocol and more details provided.
- Section 9.2.2.2 analysis method for change in clinical status of subject at Days 14 and 28 (on a 7 point ordinal scale) was updated to be in line with the FDA guidance (i.e. COVID-19: Developing Drugs and Biological Products for Treatment or Prevention).

Changes incorporated into Version 7.0 of this document.

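### SAP 9.2.2.4 names median hospital stay as the quantity compared, but rank-ANCOVA with deaths tied at the worst rank does not test medians

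*SAP*

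**What the plan says.** SAP 9.2.2.4 treats length of stay as continuous and sets out the comparison: "The median length of hospital stay will be compared between the treatment groups using a non-parametric method or a rank-ANCOVA analysis". It adds "For this analysis, the censoring rule in Section 8.6.4 will be used". There is no Section 8.6.4; the rule is in 8.7.4, where "all deaths within 42 days will be considered censored at Day 42". That section explains that censoring at Day 42 or at any later time gives the same answer, since "both correspond to giving deaths the worst rank".

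The endpoint has formal standing. The version history records that "Length of hospital stay (days) was moved from Exploratory Endpoint to Secondary Endpoint". For the secondary endpoints, SAP 8.4 says "the hierarchical test procedure, with fixed sequence approach will be used to protect the trial-wise error rate", and takes the order from 9.2.2, where length of stay comes last. SAP 9.2 adds that "All statistical tests for efficacy will be two-sided tests", at 0.05.

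Neither document states a location-shift assumption, gives an estimator for a difference in medians, or writes a null hypothesis for this endpoint. The only written hypothesis (SAP 6) concerns Day 28 mortality.

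**The concern.** The sentence names one quantity, the median, and a method that addresses another. Rank-ANCOVA and Wilcoxon-type tests take their null from equal distributions. They respond to the probability that a leronlimab patient has a better outcome than a placebo patient, with ties split. Under a pure shift that question and the median question have the same answer.

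A pure shift would move the block of tied deaths and leave its size unchanged. Here the block stays at one value in both arms and its size is expected to differ. If averted deaths become long-stay survivors, the lower half of each distribution, and so each median, is unchanged while the ranks differ.

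What is at stake is the reading of the result. A significant p-value could be reported as a difference in median hospital days when it reflects deaths, or some other part of the distribution.

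**Working it through.** **Design inputs (SAP 4).** Day 28 mortality is 45% placebo and 30% leronlimab, with 2:1 allocation, 246 + 123 completers, 260 + 130 randomized, and a "2-sided Z-test with 80% power and an overall significance level of 0.05". No figure is given for length of stay, so the sample size is reproduced first to confirm the inputs. With the unpooled Z formula, placebo n = (1.960 + 0.842)² × (0.45×0.55 + 0.30×0.70/2) / 0.15² = 7.85 × 0.3525 / 0.0225 = 123, and so 246 on leronlimab. This matches. Power at 123/246 is 80.9% by the pooled formula.

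**Assumed stay distribution (not in the documents).** In each arm 55% leave before Day 28 with the same distribution: log-normal, median 10 days, log-SD 0.6, truncated at 28. On placebo the other 45% die. On leronlimab 30% die and 15% leave on Days 29–41. Deaths are tied at 42. The planned rates are for Day 28; using them for deaths to Day 42 is a further assumption.

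**Medians.** In both arms the median is the 0.50/0.55 = 90.9th percentile of the same early-discharge distribution, which is 20 days in whole days. The medians are equal.

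**What the rank test sees.** The probability that a leronlimab patient does better, ties split, is the sum of:
- early vs early: 0.55 × 0.55 / 2 = 0.15125
- early vs dead: 0.55 × 0.45 = 0.2475
- late vs dead: 0.15 × 0.45 = 0.0675
- dead vs dead: 0.30 × 0.45 / 2 = 0.0675

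The total is 0.534, not 0.5.

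**Rejection rate by hand, 260 vs 130.** Deaths number 78 + 58.5 = 136.5, or 0.35 of 390. The null variance with the tie correction is 391 / (12 × 260 × 130) × (1 − 0.35³) = 0.000964 × 0.957 = 0.000923, giving SE 0.0304. Then z = 0.03375 / 0.0304 = 1.11, and the rejection probability is Φ(1.11 − 1.96) ≈ 0.20.

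**Simulation (4000 trials per scenario, Wilcoxon, two-sided 0.05, 260 vs 130; ranges cover repeated runs).**

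| Deaths, leronlimab vs placebo | Medians (days) | Rejects, taken alone |
|---|---|---|
| 30% vs 45% | 20 vs 20 | 20–22% |
| 20% vs 45% | 20 vs 20 | 43–47% |
| 30% vs 40% | 17 vs 17 | 10–12% |
| 15% vs 30% | 14 vs 14 | 11–13% |
| identical arms | equal | about 5% |

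A separate set of assumptions used 246 vs 123, median 14 days in both arms, and uniform stays below and above it. It gave 23% for deaths 30% vs 45%, 12% for 20% vs 30%, and 4.8% for identical arms. A linear model on ranks (rank-ANCOVA without covariates) agreed with Wilcoxon to within 0.001. With deaths equal at 30% and leronlimab stays shorter only below the common median, the test rejected 52% of the time, so the mismatch is not confined to deaths.

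**Effect of the fixed sequence.** The first secondary endpoint in 9.2.2 is reaching category 6 or higher, meaning out of hospital, at Days 14 and 28. In the table's scenarios discharge by each day has the same probability in both arms, so that endpoint is a true null. With discharge counted as category 6 or higher and an unadjusted two-proportion Z-test as the gate, the joint probability of passing the gate and a significant length-of-stay test, for deaths 30% vs 45%, is:
- both days required: about 1%
- one specified day required: about 2.5–3%
- either day sufficient: about 4–5%

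The SAP does not say how the two days combine. The other unequal-death scenarios also stayed below 5%. Adding the remaining earlier secondary endpoints can only lower the rate.

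**The case against.** The strongest reply is that the figures of 20% and above are ungated. A reader might infer from them that the trial-wise error, or the error of this controlled endpoint, is about four times nominal. The documents do not support that. Length of stay is tested last, and in the scenarios with equal medians and equal early discharge the first gate is a true null, so the joint rate is 5% or less. The test also holds its level for the null of equal distributions. This objection stands in full and limits the point to one of target and interpretation.

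A reader might also take low power despite different medians as further proof. In one such case, with medians of 23 vs 32 days, the rank test had 12.5% power, but a pooled median test on the same data had about 10%. A true median test does no better, so that argument fails.

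Two replies stand in part. The SAP leaves the alternative to rank-ANCOVA unnamed, and a median test would fit the words; but rank-ANCOVA is the only method named, and 8.7.4 justifies its rule by ranks. The worst-rank intent is indeed disclosed in 8.7.4; that makes the word median in 9.2.2.4 harder to reconcile with the method, because nothing restates the comparison as one of ranks.

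Finally, the rates depend on assumed stays, and equal medians here require averted deaths to become late discharges. The exact percentages are illustrative. That the rate can exceed 5% at equal medians does not depend on one chosen shape.

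**Conclusion.** The concern holds as a mismatch between the stated target and the named test. With planned death blocks of about 45% and 30% at one value, a pure shift is impossible, and a rank-based p-value is not a p-value for a difference in medians. Taken alone, the test rejects about 20% of the time at equal medians with those death rates, and 10% to 47% over the other equal-median scenarios in the table, against about 5% when the distributions are equal.

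No inflation of the trial-wise error has been shown. The correction still matters because a formal length-of-stay result requires the earlier secondary endpoints, including Day 14 mortality, to succeed. A mortality difference is then likely, and a rank result can reflect deaths while being described as shorter median stay. The primary analysis and the sample size are unaffected.

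**What to change.** In SAP 9.2.2.4, before unblinding:

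1. Replace the opening of the comparison sentence with: *The distribution of length of hospital stay, with death ranked as the worst outcome, will be compared.*
2. Name rank-ANCOVA as the single test, drop the open alternative, and state the null as equal distributions in the two arms.
3. Report the matching estimate with a 95% CI: the probability that a leronlimab patient has a better outcome than a placebo patient (ties split), or the win odds.
4. Show medians and mortality by arm descriptively, say whether deaths are included in the medians, and attach no p-value or claim to the difference in medians.
5. Correct the cross-reference from 8.6.4 to 8.7.4.

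The cost is a few lines of SAP text and one extra estimate. The death rule, testing order and sample size stay as they are. The small downside is that the inferential effect is no longer expressed in days.

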### 9.2.3 Exploratory Outcome Measures (Endpoints)

## 9.2.3.1 All-Cause Mortality at Day 42

All-cause mortality at Day 42 will be summarized descriptively by treatment group. Similar analysis methods used for the primary endpoint will be applied to analyze the data from this endpoint

9.2.3.2 Change in clinical status of subject at Days 3 and 7 (on a 7 point ordinal scale)

Change in clinical status of subject at Days 3 and 7 will be summarized descriptively and compared using ANCOVA adjusting for stratification factors.

If the Normality assumption is not met, a non-parametric method or a rank –ANCOVA analysis i.e., an ANCOVA analysis on rank-transformed data will be used.

9.2.3.3 Change from baseline in Sequential Organ Failure Assessment (SOFA) score at Days 3 and 7

Change from baseline in Sequential Organ Failure Assessment (SOFA) score at Days 3 and 7 will be summarized descriptively and compared using ANCOVA adjusting for stratification factors. If the Normality assumption is not met, a non-parametric method or a rank –ANCOVA analysis i.e., an ANCOVA analysis on rank-transformed data will be used.

9.2.3.4 Proportion of subjects extubated within 14 days of start of study treatment

Proportion of subjects extubated within 14 days of start of study treatment will be summarized and compared using Logit model, adjusting for stratification factors.

- 9.2.3.5 Proportion of subjects admitted into an intensive care unit (ICU) after randomization Proportion of subjects admitted into an intensive care unit (ICU) after randomization will be summarized and compared using Logit model, adjusting for stratification factors.
- 9.2.3.6 Proportion of subjects requiring initiation of mechanical ventilation after randomization

Proportion of subjects requiring initiation of mechanical ventilation after randomization will be summarized and compared using Logit model, adjusting for stratification factors.

9.2.3.7 Change from baseline in Sequential Organ Failure Assessment (SOFA) score at Day 14

Change from baseline in Sequential Organ Failure Assessment (SOFA) score at Day 14 will be summarized descriptively and compared using ANCOVA adjusting for stratification factors. If the Normality assumption is not met, a non-parametric method or a rank –ANCOVA analysis i.e., an ANCOVA analysis on rank-transformed data will be used.

## 9.2.3.8 Length of ICU stay (days)

Length of ICU stay will be summarized descriptively and compared using ANCOVA adjusting for stratification factors.

If the Normality assumption is not met, a non-parametric method or a rank –ANCOVA analysis i.e., an ANCOVA analysis on rank-transformed data will be used.

## 9.2.3.9 Duration (days) of mechanical ventilation (if applicable)

Duration of mechanical ventilation will be summarized descriptively and compared using ANCOVA adjusting for stratification factors.

If the Normality assumption is not met, a non-parametric method or a rank –ANCOVA analysis i.e., an ANCOVA analysis on rank-transformed data will be used.

#### 9.2.3.10 Time to clinical recovery

Time to clinical recovery will be compared between the treatment groups using Cox proportional hazards model with the stratification factors in the model. Kaplan-Meier analysis will also be used to depict the median time (days) to clinical recovery for the treatment groups. The likelihood score test in the Cox proportional hazards model (which is the equivalent of the Log Rank test) will be used to compare the time to return to normal activity between the treatment groups.

### 9.2.3.11 Change from baseline in pulse oxygen saturation (SpO2) at Days 3, 7, and 14

Change from baseline in pulse oxygen saturation (SpO2) at Days 3, 7, and 14 will be summarized descriptively and compared using ANCOVA adjusting for stratification factors.

If the Normality assumption is not met, a non-parametric method or a rank -ANCOVA analysis i.e.,

an ANCOVA analysis on rank-transformed data will be used.

9.2.3.12 Change from baseline in National Early Warning Score 2 (NEWS2) at Days 3, 7, and 14 Change from baseline in National Early Warning Score 2 (NEWS2) at Days 3, 7, and 14 will be summarized descriptively and compared using ANCOVA adjusting for stratification factors. If the Normality assumption is not met, a non-parametric method or a rank –ANCOVA analysis i.e., an ANCOVA analysis on rank-transformed data will be used.

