During visits conducted at the subject's home, the visiting nurse (or trained site staff) will administer study drug (if applicable), monitor subjects for safety, perform blood draw, and all other assessments related to study outcomes measures. All procedures (except chest radiograph or CT scan) listed under the schedule of assessments can be performed by visiting nurse at visits taking place in the subject's home.

CONFIDENTIAL Page 50 of 108

[figure not shown]

Table 4-2: Schedule of Assessments

Procedure/Assessments	Screening Visit	Treatment Phase				Follow-Up		
Visit	V1	V2 (Pre-Rx)	[17] (Post-Rx)	V3	V4	V5 (EOT)	V6	V 7
Day		Da	y 0	Day 3	Day 7	Day 14	Day 28	Day 42
Window Period			of the Screening sit	3(±1) days after V2	7(±1) days after V2	7(±1) days after V4	14(±3) days after EOT Visit	28(±3) days after EOT Visit
Informed Consent [1]	X							
Eligibility Evaluation [2]	X							
Subject Demographics	X							
Medical History [3]	X							
Physical Examination	X	X		X[4]	X[4]	X	X[4]	X [4]
Vital Signs [5]	X	X	X	X	X	X	X	X
Clinical Status - Ordinal Scale Assessment	X	X		X	X	X	X	
PaO2/FiO2, if intubated	X	X		X	X	X		
Pulse oxygen saturation (SpO2)	X	X		X	X	X		
Positive End-Expiratory Pressure (PEEP), if intubated	X	X		X	X	X		
Sequential Organ Failure Assessment (SOFA) score, if intubated [6]		X		X	X	X		
National Early Warning Score 2 (NEWS2) Assessment [7] [19]	X	X		X	X	X		
Assessment of clinical recovery [8]				X	X	X		
ECG	X					X		
Laboratory tests:								
Complete Blood Count [9]	X			X	X	X		X
Biochemistry [10]	X			X	X	X		X
Coagulation Indices [11]	X			X	X	X		X

CONFIDENTIAL Page 51 of 108

Procedure/Assessments	Screening Visit	Treatment Phase					Follow-Up	
Visit	V1	V2 (Pre-Rx)	[17] (Post-Rx)	V3	V4	V5 (EOT)	V6	V 7
Day		Da	y 0	Day 3	Day 7	Day 14	Day 28	Day 42
Window Period			of the Screening	3(±1) days after V2	7(±1) days after V2	7(±1) days after V4	14(±3) days after EOT Visit	28(±3) days after EOT Visit
Serum/Urine Pregnancy Test [12]	X					X		
Urinalysis [13]	X			X	X	X		X
CD3+, CD4+ and CD8+ T cell count		X		X	X	X		
CCR5 receptor occupancy for Treg and macrophage [19]		X		X	X	X		
Serum cytokine and chemokine levels [19]		X		X	X	X		
CCR5 Gene Polymorphisms [14] [19]		X		X	X	X		
Nasopharyngeal Swab Sample Collection [15] [19]	X	X		X	X	X	X	X
Chest radiograph or CT (if clinically indicated) [16]	X					X		
Randomization [18] [19]		X						
PRO 140 (700 mg) [or Placebo[19]] Administration		2	Υ .		X			

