## 3.3 Exploratory Outcome Measures (Endpoints)

- All-cause mortality at Day 42
- Change in clinical status of subject at Days 3 and 7 (on a 7 point ordinal scale)
  - A 7-category ordinal scale of patient health status ranges from: 1) Death; 2) Hospitalized, on invasive mechanical ventilation or extracorporeal membrane oxygenation (ECMO); 3) Hospitalized, on non-invasive ventilation or high flow oxygen devices; 4) Hospitalized, requiring supplemental oxygen; 5) Hospitalized, not requiring supplemental oxygen; 6) Not hospitalized, limitation on activities; 7) Not hospitalized, no limitations on activities.
- Change from baseline in Sequential Organ Failure Assessment (SOFA) score at Days 3 and
   7.
- Proportion of subjects extubated within 14 days of start of study treatment.
  - Note: This applies only for subjects who were intubated at the time of randomization
- Proportion of subjects admitted into an intensive care unit (ICU) after randomization
   Note: This applies only for subjects who were hospitalized but not in an intensive care unit (ICU) at the time of randomization
- Proportion of subjects requiring initiation of mechanical ventilation after randomization
   Note: This applies only for subjects who does not require mechanical ventilation at the time of randomization
- Change from baseline in Sequential Organ Failure Assessment (SOFA) score at Day 14.
- Length of ICU stay (days)
- Duration (days) of mechanical ventilation (if applicable)
- Time to clinical recovery
  - Time from initiation of the study to discharge or to normalization of fever (defined as  $<36.6^{\circ}$ C from axillary site, or  $<37.2^{\circ}$ C from oral site or  $<37.8^{\circ}$ C from rectal or tympanic site), respiratory rate (<24 bpm while breathing room air), alleviation of cough (defined as mild or absent in a patient reported scale of 0=absent, 1=mild, 2=moderate, and 3=severe) and resolution of hypoxia (defined as  $SpO2 \ge 93\%$  in room air or  $P/F \ge 300$  mmHg). All these improvements must be sustained for at least 24 hours.
- Change from baseline in pulse oxygen saturation (SpO2) at Days 3, 7, and 14
- Change from baseline in National Early Warning Score 2 (NEWS2) at Days 3, 7, and 14.
   This score is based on 7 clinical parameters (respiration rate, oxygen saturation, any

supplemental oxygen, temperature, systolic blood pressure, heart rate, level of consciousness).

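### Time to clinical recovery (exploratory) has no rule for deaths; under the default analysis Kaplan-Meier overstates recovery, most in the arm with more deaths

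*SAP*

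**What the plan says.** SAP 3.3 defines the event as recovery by either of two routes: "Time from initiation of the study to discharge or to normalization of fever" together with respiratory rate, cough and oxygenation criteria held for 24 hours. Death is not mentioned.

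SAP 9.2.3.10 gives the analysis: "Time to clinical recovery will be compared between the treatment groups using Cox proportional hazards model with the stratification factors in the model". It continues: "Kaplan-Meier analysis will also be used to depict the median time (days) to clinical recovery for the treatment groups". The score test from the Cox model then "will be used to compare the time to return to normal activity between the treatment groups".

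The only rule for deaths is SAP 8.7.4: "For analyses of length of stay (i.e., ICU or hospitalization) or duration of mechanical ventilation all deaths within 42 days will be considered censored", with Day 42 as the censoring time. Its stated reason is that censoring at Day 42 or at any later time gives the same answer, because "both correspond to giving deaths the worst rank". Time to clinical recovery is not in its scope.

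Protocol 8.10.4 names the Cox model for time-dependent data and adds no death or competing-risk rule. SAP 8.3 prescribes multiple imputation for missing efficacy data but does not mention death or event times.

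Protocol Table 4-2 schedules the assessment of clinical recovery at V3, V4 and V5 only, that is Days 3, 7 and 14. Protocol 7.20 likewise has hospital stay last assessed at V5.

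**The concern.** A patient who dies unrecovered can never recover. An unmodified Cox or Kaplan-Meier analysis censors that patient at death and treats later recovery as still possible. The sample-size section assumes Day 28 mortality of 45% on placebo and 30% on leronlimab, so death would be a frequent competing event and probably an unequal one.

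Two things follow. One minus Kaplan-Meier, and the median read from it, estimate recovery in a setting where nobody dies; they overstate actual recovery, most in the arm with more deaths. The Cox ratio compares recovery rates among patients still alive and unrecovered, which need not agree with the comparison of proportions who recover.

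The SAP is also inconsistent with itself. The same death takes the worst rank for hospital stay, yet discharge is one of the two routes to recovery, and for recovery that death would by default leave the risk set as if recovery were still possible. Because the rule is unstated, it could be chosen after the data are seen.

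Separately, the test sentence names return to normal activity. That is not an endpoint of this trial; Protocol 1.4.2.18 lists it for the earlier study in mild-to-moderate disease.

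**Working it through.** **The plan's own figure.** The documents give no figure for time to recovery. The sample-size section supplies the mortality rates and arm sizes, and it reproduces. With an unpooled two-proportion Z-test, 2:1, two-sided 0.05 and 80% power, the placebo arm needs (1.960 + 0.842)² × (0.45×0.55 + 0.30×0.70/2) / 0.15² = 123. The total is 3 × 123 = 369, as stated.

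**Illustration 1: equal recovery by Day 28, unequal deaths.** From the documents: Day 28 mortality of 45% and 30%. Assumed: 40% recovered by Day 28 in both arms, and constant hazards.

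For recovery proportion r and death proportion m at Day 28, the total hazard is −ln(1 − r − m)/28. The recovery hazard is r/(r + m) of that.

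- More deaths: −ln(0.15)/28 = 0.0678 per day; × 0.40/0.85 = 0.0319.
- Fewer deaths: −ln(0.30)/28 = 0.0430 per day; × 0.40/0.70 = 0.0246.
- Cox ratio with deaths censored: 0.0319/0.0246 = 1.30 in favour of the arm with more deaths (0.77 with the arms exchanged).
- One minus Kaplan-Meier at Day 28, 1 − exp(−28 × hazard): 0.59 and 0.50, against a true 0.40 in each arm. The overstatement is 0.19 and 0.10.
- Kaplan-Meier medians, ln 2/hazard: 21.7 and 28.2 days. The arm with more deaths looks about 6.5 days faster, although equal proportions recover by Day 28.

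Keeping deaths in the risk set as not recovered to the end of the window gives, for the same model:

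| Window ends | Truly recovered, more deaths / fewer deaths | Hazard ratio, arm with more deaths vs other | Arms exchanged |
|---|---|---|---|
| Day 14 | 28.8% / 25.8% | 1.15 | 0.87 |
| Day 28 | 40.0% / 40.0% | 1.03 | 0.97 |
| Day 42 | 44.3% / 47.8% | 0.95 | 1.06 |

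The ratio moves with the window because this model equalises recovery at Day 28 only.

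**Illustration 2: equal recovery hazard, unequal deaths.** Assume 0.03 per day in both arms. The Cox ratio is then 1 and is not shifted. One minus Kaplan-Meier at Day 28 is 0.57 in both arms, while the true proportion recovered is 0.45 with 30% mortality and 0.39 with 45%. Kaplan-Meier hides the deficit.

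**Illustration 3: deaths only among patients who would not have recovered.** This used 246 and 123 patients, a 28-day window, 40% or 50% recovering with identical timing in both arms, and 400 replicates per scenario.

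- Deaths censored, more deaths on leronlimab: 1.22 to 1.29, p<0.05 in 19% to 33% of replicates.
- Deaths censored, more deaths on placebo: 0.83 to 0.81, p<0.05 in 19% to 28%.
- Deaths kept to the end of the window: 1.00 to 1.02, p<0.05 in 5% to 6.5%.
- Equal mortality of 30%: about 1.01 under either method.

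**The case against.** The case on the other side has four parts.

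**The SAP does not say deaths are censored at the death date.** A reader might infer that it does. It is silent, and censoring is only what the named methods do by default. This stands, and the point is worded accordingly. Silence still leaves the rule open.

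**The 1.30 is not an estimation error in the Cox model.** Fixing 40% recovery in both arms while mortality differs builds in recovery hazards of 0.0319 and 0.0246, and Cox returns their ratio correctly. This stands. The ratio answers a different question from who recovers, and Illustration 2 shows that it need not move at all. What does not depend on that relation is the Kaplan-Meier overstatement.

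**A reader might infer that applying the 8.7.4 rule reverses the direction of the result.** The documents do not support that. In the illustration the two methods fall clearly on opposite sides of 1 only with a Day 42 window, and recovery is scheduled for assessment only to Day 14. With a Day 14 window the value is 1.15, the same direction as 1.30.

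**Little depends on this endpoint.** It is exploratory and outside the fixed-sequence testing. Outcomes that include death already carry the main conclusions: Day 28 mortality, category 6 or higher, and the 7-category scale. This stands and limits the weight of the point. It does not make the Kaplan-Meier curve or median readable as recovery in a trial planned around 30% to 45% mortality.

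**Conclusion.** The gap is real. Time to clinical recovery has no death rule, and the SAP's own worst-rank principle is not carried over to it. Under the default analysis the Kaplan-Meier curve and median overstate recovery, most in the arm with more deaths. The Cox ratio is cause-specific and may differ from the comparison of proportions who recover.

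Under the stated assumptions the size is a hazard ratio of about 1.30 against about 1.03 with deaths kept as not recovered to Day 28. The 40% recovery and constant hazards are assumptions, and the second value depends on the window. At the planned mortality rates the distortion works against leronlimab (0.77). It would favour leronlimab only if leronlimab had more deaths.

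No primary or secondary conclusion and no type I error control is affected. The point is worth correcting because an exploratory recovery result could otherwise be misread, and because the test sentence names the wrong variable.

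**What to change.** - Extend SAP 8.7.4 to time to clinical recovery: patients who die unrecovered stay in the risk set and are censored at the end of one stated recovery window.
- Set that window to match the assessment schedule: Day 14 as scheduled, or a later day only if discharge dates are captured to that day.
- Replace the Kaplan-Meier recovery curve and median in SAP 9.2.3.10 with the cumulative incidence of recovery, with death as a competing event.
- In the score-test sentence, change return to normal activity to clinical recovery.

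The cost is a few sentences in the SAP. No change to sample size or alpha is needed, and no new data if the window is Day 14.
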